COGNITIVE TRAINING TO REDUCE IMPULSIVITY IN HIV-INFECTED COCAINE USERS

NCT02909101

Study Protocol with Statistical Analysis Plan

VERSION DATE: April 13, 2018

Specific Aims

This study tests the feasibility and preliminary efficacy of a computerized cognitive training program to improve working memory and decrease impulsivity (delay discounting) among HIV-infected individuals. The specific aims are to

- (1) Investigate the effects of the cognitive training intervention on working memory (primary outcome) and delay discounting (secondary outcome) in HIV-infected persons;
- (2) Establish the acceptability of computerized cognitive training among HIV-infected past or present cocaine users; and
- (3) Examine the effect of cognitive training on HIV risk behaviors, including cocaine use, risky sex, and medication adherence (exploratory outcomes).

We hypothesize that: (1) Participants assigned to active cognitive training (ACT), compared to those in the attention-matched control group (CON), will have greater improvements in working memory and reductions in delay discounting; (2) Participants assigned to ACT, compared to those in CON, will have greater reductions in HIV risk behaviors, including improvements in medication adherence.

Study design

The proposed study will test the efficacy of a cognitive training program to improve working memory in a sample of HIV-infected cocaine users. We will evaluate the effects of this cognitive training intervention on working memory, delay discounting, and HIV risk behaviors. We will first screen participants for eligibility. Eligible participants will be assigned to one of two groups (ACT or CON) and will complete 48 training sessions over 10 weeks. Participants assigned to ACT will complete computerized games designed to enhance working memory, while those assigned to the attention-matched CON will complete games that use other brain attributes. We will be using a web-based program, Lumosity (Lumos Labs, Inc.; <http://www.lumosity.com>). Lumosity is available to the public and offers user-friendly cognitive training games targeting different brain areas. We have developed a contract with Lumosity tailoring the website to fit our study's needs. All participants will complete assessments at baseline, post-training, and 1-month follow-up to evaluate the impact of the training program. Staff members conducting assessments will be blinded to treatment condition in order to ensure no biases occur during testing.

Eligibility criteria

The sample will be open to HIV-infected men and women aged 18-60 years of all racial/ethnic groups who are currently on antiretroviral medications for >3 months and are cocaine users. Cocaine use will be defined as lifetime regular crack/cocaine use lasting >1 year, cocaine-type stimulant use disorder, and cocaine as the principal substance of abuse. Exclusion criteria will include pregnancy; English non-fluency or illiteracy; ≤ 8th grade education; serious and unstable neurological disorders; unstable serious mental illness or acute psychiatric distress; and impaired mental status. Women who are pregnant will be excluded because of the known effects of pregnancy on neuropsychological functioning (including deficits in memory and executive control). To reduce potential attrition, individuals who state they are planning to move away from the area within the next 3 months and individuals without stable housing will be excluded.

Recruitment

Both clinic- and community-based recruitment strategies will be used. Participants will learn about the study via flyers in clinics, community-based organizations that serve HIV-positive individuals, and participant referrals. Clinic recruitment will occur at local infectious diseases clinics. Patients may also self-refer in response to flyers and brochures displayed in the waiting

area and exam rooms. We may also run advertisements in local newspapers and online. Finally, participants may be recruited through our lab's repository contact database (IRB Pro00047043).

Prescreening

Regardless of how potential participants are informed of the study, interested individuals will complete a pre-screening with a member of the research staff to determine preliminary eligibility. This pre-screening will occur in person or over the telephone.

Cognitive Training Study

Screening Visit. If potentially eligible after prescreening, participants will be invited to complete a 2-3 hour screening visit in our laboratory to verify eligibility criteria. The informed consent process will occur at the beginning of this visit, followed by a breathalyzer to ensure that the participant is not acutely intoxicated. The initial part of the screening visit will include the urine drug testing and pregnancy testing if indicated. Participants will then complete questionnaires and clinical interviews to assess HIV and other medical history, substance use, and mental health (**Table 1**). Trained

research assistants will administer clinical interviews and neuropsychological tests of working memory. Additional questionnaires will be administered using audio computer-assisted self-interview (ACASI) technology. The urine toxicology screen will be used to verify self-reports of recent use of cannabis, cocaine, stimulants, opioids, and benzodiazepines.

In-person Interview and Testing. In-person interview and testing (lasting approximately 90 minutes) will be conducted by trained research personnel. Interviews will assess substance use and impairment, psychiatric history, HIV testing, staging and treatment history, medication adherence, substance use, sexual behaviors, and psychiatric history.

ACASI. Questionnaires will be programmed using QDS™ software. The computer will display one question at a time, and participants will respond using a mouse. For patients who prefer not to read, the computer will read the questions and responses using prerecorded sound files. The ACASI will last approximately 30 minutes will include items related to demographics, anxiety and depression, HIV symptoms, stimulant craving, and medical history.

Baseline Assessment. Eligible participants will be invited back on a separate day for a 3-hour baseline assessment. At the beginning of this visit, participants will complete a breathalyzer, urine drug testing and pregnancy testing if indicated. Participants will then complete an assessment battery of standardized measures that includes face-to-face interviews, questionnaires, decision making tasks, and neuropsychological testing (**Table 2**).

Neurocognition. A 60-minute comprehensive neuropsychological battery will assess functioning across performance domains and estimates premorbid intellectual functioning. All tests have excellent clinical validity with large national norming samples and will be scored using standard procedures.

Table 1. Eligibility Screening Measures	
Construct	Instrument(s)
In-person Interview and Testing	
Substance Use & Impairment	Addiction Severity Index-LITE ^{1,2}
Substance Use Disorders	Structured Clinical Interview for DSM-5 (SCID-5) Module E ³
Psychiatric history	SCID-5 Modules A and B ³
HIV Testing and Staging	HIV Cost and Services Utilization Study ⁴
Literacy	Wide Range Achievement Test-4 Word Reading Subtest ⁵
ACASI	
Patient Characteristics	Demographics
Anxiety/Depression	Brief Symptom Inventory ⁶
HIV Symptoms	HIV Symptoms Index ⁷
PTSD Symptoms	Post-Traumatic Stress Disorder Checklist-5 ⁸
Craving	Stimulant Craving ⁹
Medical History	Veteran's Aging Cohort Study ¹⁰
Trait Impulsivity	Barratt Impulsivity Scale Version 11 ¹¹
Sensation Seeking	Sensation Seeking Survey Version V ¹²

In-person interview. Trained research personnel will conduct interviews lasting approximately 30 minutes. The interview will assess HIV medication adherence, substance use, and sexual behaviors.

ACASI. The ACASI will last approximately 40 minutes and will include items related to psychiatric symptoms, food insecurity, stimulant craving, quality of life, smoking history, and sexual and drug risk.

Decision making. Several computerized tasks, lasting approximately 30 minutes, will assess distinct aspects of decision making. The Game of Dice Task (GDT) assesses decision making. In this task, a virtual die is rolled and the participant is asked to select a single number or a combination of two, three, or four numbers. If the number rolled on the die equals any of the numbers in the participant's choice, the participant will gain a specified amount of money in a fictitious bank. The participant will lose an equivalent amount from the fictitious bank if the number rolled is not equal to any of the numbers in their selection. The participant is tasked with accumulating as much money as possible in the bank, and each selection is associated with an explicit gain/loss of fictitious money. The amount of fictitious money that can be gained/lost increases as the probability of the selection occurring decreases. Risky decisions, defined as choices that have less than a 50% chance of occurring, and the frequency of alternative

Table 2. Baseline Measures

Construct	Instrument(s)
In-person Interview	
Medication adherence	ARV Adherence ^{13,14}
Sex/drug risk	Timeline Follow-back for Substance Use and Sexual Behaviors ¹⁵
HIV Risk Behaviors	HIV Risk Behavior Scale (HRBS) ¹⁶
Neurocognition	
Attention	Conners Continuous Performance Test 3 (CPT 3) ¹⁷
Executive Function	Stroop Color and Word Task ¹⁸ Trail Making Test Part B (TMT B) ¹⁹
Learning	Hopkins Verbal Learning Test-Revised (HVLT-R) Immediate ²⁰ Brief Visuospatial Memory Test-Revised (BVMT-R) Immediate ²¹
Memory	HVLT-R Delayed ²⁰ BVMT-R Delayed ²¹
Processing Speed	Trail Making Test Part A (TMT A) ¹⁹ WAIS-IV Coding ²²
Motor	Grooved Pegboard Test (GPT) ²³
Verbal Fluency	Controlled Oral Word Association Test (COWAT; FAS and Animals) ²⁴
Working Memory	Paced Auditory Serial Addition Test-100 ²⁵ WAIS-IV Letter-Number Sequencing, ²² WAIS-IV Digit Span ²²
Premorbid Functioning	Wechsler Test of Adult Reading (WTAR) ²⁶
Decision Making	
Decision Making	Game of Dice Task ²⁷
Delay discounting	Monetary Choice Questionnaire ²⁸
Abstract reasoning	Wisconsin Card Sorting Test-64 (WCST) ²⁹
ACASI	
Psychiatric Symptoms	Symptom Checklist 90-Revised (SCL-90) ⁶
Food Insecurity	Household Food Insecurity Access Scale ³⁰
Craving	Stimulant Craving ⁹
Quality of Life	World Health Organization Quality of Life-BREF (WHOQOL-BREF) ³¹
Self-assessment	Patient's Assessment of Own Functioning Inventory ³²
Sexual/Drug Risk	Risk Assessment Battery (RAB) ³³
Nicotine Dependence	Fagerstrom Test for Nicotine Dependence (FTND) ³⁴ and smoking history
Stimulant Dependence	Severity of Dependence Scale (SDS) ³⁵

selections will be analyzed. The Monetary-Choice Questionnaire (MCQ) is a delay discounting task. Participants make 36 choices between smaller immediate rewards (ranging from \$11 to \$78) and larger delayed rewards (ranging from \$25 to \$85 and from 7 to 186 days). An individual's point of indifference where the perceived value of a smaller immediate reward is equivalent to a larger delayed reward is computed using the following hyperbolic function: $V_{\text{immediate}} = V_{\text{delayed}} / (1 + kD)$, in which V is value in dollars, D is delay in days, and k is a free parameter that determines the discount rate. The Wisconsin Card Sorting Test-64 (WCST) is used to measure abstract reasoning, concept generation, and perseverative responding. In this computerized task, participants sort cards according to one of three principles of class membership, including categories completed, perseverative responses, perseverative errors, nonperseverative errors, failure to maintain set, and efficiency of learning.

Cognitive Training Sessions. At the end of the baseline assessment, enrolled participants will be randomly assigned to either the experimental (Active Cognitive Training, or ACT) or control (or CON) conditions using simple random assignment. Participants will be trained to use Lumosity after the baseline assessment. Research staff will provide instructions and guide them through the first training session. Participants will then immediately begin completing sessions at home the following day.

Schedule of training sessions. All enrolled participants will be asked to complete 48 training sessions over 10 weeks. The sessions will last approximately 20-30 minutes and will be completed at home or wherever the participant can obtain computer access. If the participant has no means of accessing a computer, sessions can be completed in-person in the research laboratory. Participants will be encouraged to complete 6 sessions a week, 1 per day, to reach a total of 48 by the end of the 10-week period. While each group will complete the same number of sessions to control for possible dosage effects, the content of the sessions will vary by study group. Each condition will include 8 unique Lumosity games.

Active Cognitive Training (ACT). Sessions will include games from Lumosity that are designated as targeting working memory. One training session will be comprised of a randomly generated subset of 4 of the 8 working memory games, each played twice back-to-back.

Control Training (CON). The sessions will be in the same format as the ACT group, but will utilize other Lumosity games that do not target working memory. These games will be the same length as the working memory games and participants will complete the same number of randomly generated games per session (4 of the 8 games, played twice back-to-back).

Post-training Assessment. After completing the 48th training session, or at the end of the 10-week training window, participants will complete a post-training assessment. This 3-hour visit will occur within 1 week of the final training session and will consist of a battery identical to the baseline assessment. Alternate forms of neuropsychological tests involving memory will be used to avoid effects related to repeated testing. Participants will also complete a process measure to describe their experiences of the intervention and provide feedback on perceived benefits, barriers to completing sessions, and the length, number, and content of sessions. This assessment includes open-ended questions and ratings of satisfaction and helpfulness.

One-month Follow-up Assessment. One month after the post-training assessment, participants will complete a follow-up assessment. This 3-hour visit will consist of a battery identical to the baseline assessment. Alternate forms of neuropsychological tests involving memory will be used to avoid any effects related to repeated testing.

Human Subjects Protections

Rationale for participant selection. The purpose of this study is to examine the impact of cognitive training on neurocognitive performance, including working memory and delay

discounting, on persons with HIV infection and co-occurring cocaine abuse. Therefore, participants will be HIV-positive cocaine users.

Evaluation of benefits, risks, and discomforts. A direct benefit for participants who complete the study may be improved cognitive function as a result of the cognitive training exercises administered at each session. The risk/benefit ratio for this study is relatively low and there are few expected risks associated with participation in this study. All data collection procedures are minimally invasive. All procedures will be performed by research personnel who are trained in the study procedures to minimize risks, discomforts, and adverse events. We expect that the results of this study will inform new treatments for HIV-infected individuals by providing empirical support for a low-cost intervention to improve neuropsychological functioning. Given the minimal amount of risk associated with participation, coupled with the potential scientific gains, we believe that the risk to participants is reasonable.

The potential risks associated with this study fall into the following two categories: confidentiality and emotional distress.

1. Confidentiality. The following precautions will protect the privacy of participants and maintain confidentiality of research data: (1) All staff will be well trained in confidentiality and data security procedures. (2) Privacy will be maintained by conducting all study procedures in closed and soundproof rooms. (3) Each participant will be assigned a unique study ID number, and all data will be de-identified and coded with ID numbers only. The key linking participant names and ID numbers will be stored in a separate password protected document on the secure server maintained by the Department Psychiatry & Behavioral Science, and only essential study staff will have access to it. (4) Data will be securely stored in locked file cabinets in locked offices and in password protected documents on password protected computers and secure servers. Access to data storage areas and computers will be restricted. (5) Analysis will occur on de-identified data only. (6) Data will only be stored for as long as necessary to complete the study, and for adherence to university, hospital, and federal regulations. Thus, while we acknowledge that a breach of confidentiality is possible, the likelihood is very low.

In the event that a subject indicates potential harm to self or others during the research study, this will need to be addressed appropriately and with sensitivity. Any disclosures will be handled within the framework of existing legal mandates, clinical practice, and social norms. Consistent with standard clinical practice, when possible, disclosures will be discussed with the participant to determine the best management alternatives. This may include notifying family members, referring to medical treatment, calling emergency services, or escorting the participant to the Emergency Department at Duke Hospital. When required by law, the Police Department and/or the Department of Social Services will be notified. [name] (the PI) and [name] (co-I) are both licensed clinical psychologists with experience managing such cases.

2. Emotional distress. Some participants may experience discomfort or embarrassment related to providing urine samples and answering questions about substance use and other personal behaviors. Participants will be informed prior to the assessment that they may choose to skip any question or procedure they find uncomfortable. All research staff will be extensively trained on study procedures, including the conduct of interviews that elicit personal information, and the importance of being sensitive to and respectful of all participants. If distress does occur, research staff will be trained on how to identify and manage it, and when to terminate an interview. If necessary, the participant will be referred to mental health treatment. It is important to note that, as part of the informed consent procedure, all individuals will be notified that if they express direct threats of harm to self or others, the study team may exercise the right to arrange care or intervention for the individual if the situation is appraised to constitute an emergency.

All project staff will be trained to immediately consult with the PI or back-up person in the event that any applicant or enrolled participant appears to be experiencing psychological or physical distress. Indications of the need for this might include hearing the individual making comments or asking questions that suggest cognitive impairment; noting that the individual appears to be highly anxious, depressed, or withdrawn; or having a belief that the individual may be contemplating harming himself/herself or another person. Responses on select questions (such as the suicide assessment on the SCID assessment) that indicate potential risk of harm to self or others also require immediate consultation. In the event that cases such as this are brought to the PI or back-up person, she will assist the staff member in identifying appropriate community resources and will oversee the process of seeking outside assistance for this individual. Multiple levels of back-up support for research personnel will be developed. The research team includes two licensed clinical psychologists; they will be available to intervene and, when necessary, ensure that appropriate services are received. In the event of clinical deterioration, assessors may perform an initial risk assessment, but any clinical intervention or actions will be conducted by [name], [name], or a designated back-up person.

Consent processes and documents. Prior to the initiation of any clinical research procedures, designated research staff will describe the study's purpose, all procedures, and risks/benefits and review the informed consent document with the participant. Participants will be provided ample time to read the consent, ask questions, and deliberate their decision. If they choose to participate they will then provide written informed consent. Participants will also sign a release of information form to allow study staff to review their medical record at any other facility where they have obtained HIV and/or other medical care, if applicable. Participants will be given copies of these documents. Participants will provide informed written consent for each of the two parts of the study. These documents will be stored in locked file cabinets in locked offices separate from other data collected in this study.

Compensation. Participants will receive compensation for each of the study visits. Participants may earn up to \$441. Participants will be compensated \$50 for the screening visit, \$75 for the baseline assessment, \$65 for the post-training assessment, and \$85 for the 1-month follow-up. For the 48 training sessions, participants will be compensated \$2 for each completed session, and will earn a bonus after every 6 sessions. Participants will earn a \$5 bonus after completing 6, 12, 18, and 24 sessions; a \$10 bonus after 30 and 36 sessions; and a \$15 bonus after 42 and 48 sessions. Total potential earnings for completing all sessions are \$166.

Compensation will be in the form of a reloadable debit card. In addition, we will offer bus tokens (worth \$2 for round-trip) or parking passes (worth up to \$6) to participants who require assistance.

Safety assessment. Our assessment batteries include several measures intended to assess for safety, including breathalyzer for alcohol intoxication and mental status exam. Adverse events (AEs) will be monitored throughout the study. Each AE will be classified as serious or non-serious, and appropriate reporting procedures will be followed.

Statistical analyses

Initial analyses will confirm the psychometric properties of the assessments, and scale scores will be constructed. Data distributions will be checked to determine if they meet the assumptions of the analytic models, and transformations will be performed when necessary to improve distributional qualities. Preliminary analyses will compare study groups on demographic and other characteristics obtained in the screening and baseline assessments to identify possible failures in random assignment, which would be statistically controlled for in subsequent analyses. We will also test for any differential attrition across groups at both follow-ups. All analyses will be repeated with other substance use added as a covariate.

Hypothesis testing (Aim 1). Using an intent-to-treat analysis, we will investigate the differential impact of condition (ACT vs. CON) at the post-training assessment by performing a 2 (Condition) by 2 (Time) general linear model (GLM) analysis on the main outcome measures of working memory (mean T-score on the 3-test battery) and delay discounting (natural log k-value). Time will be a within subjects factor defined by baseline versus post-training assessment. The analysis will be repeated, adding the 1-month follow-up in a 2 (Condition) by 3 (Time) GLM to detect differential effects of the two conditions on outcomes through the follow-up period. Significant interactions of Condition and Time are predicted. To examine the specificity of the cognitive training intervention, we will use the same models to test for group differences on performance in other cognitive domains (e.g., verbal fluency, processing speed) and other measures of decision making (i.e., contingency learning, risk taking propensity).

Additional analyses will be restricted to participants who were randomized to ACT. First, we will examine predictors of treatment response (moderators) based on sample characteristics. We will use linear regression to predict change in the main outcome variables (working memory and delay discounting), with potential moderators entered separately as predictors. Second, we will use linear regression to evaluate the effect of treatment dosage (number of sessions completed) on change in the outcome variables. Finally, if intervention effects are identified on main outcomes, we will test whether effects were mediated by performance on the working memory training modules using bootstrap analyses.³⁶⁻³⁸

Acceptability (Aim 2). We will examine participant ratings of satisfaction with the cognitive training intervention, as well as their perception of its benefits and barriers to completing sessions. The intervention will be considered acceptable if participant ratings are high (>3.5 on a 5-point scale). We will also calculate the average number of sessions completed and determine the proportion of participants who successfully completed the intervention (defined as completing ≥36 of the 48 total sessions). The intervention will be considered acceptable to the target population if ≥80% complete the intervention.

Exploratory analyses (Aim 3): To investigate the impact of the intervention on risk behaviors, we will use the same GLM models described above to test for differences by condition on cocaine use (number of days of use), sexual risk (HRBS sex risk score), and adherence to ARVs (percent medication adherence).

Clinical Trials Registration

This study is registered at <http://www.ClinicalTrials.gov> (Identifier: NCT: NCT02909101).

References

4. RAND Corporation. *HIV Cost and Services Utilization Study (HCSUS) baseline questionnaire*. Santa Monica, CA: RAND Corporation; 2007.
5. Wilkinson GS, Robertson GJ. *Wide Range Achievement Test-4 (WRAT-4)*. Lutz, FL: Psychological Assessment Resources.
6. Derogatis LR. *Brief Symptom Inventory: Administration, Scoring, and Procedures Manual*. 3rd ed. Minneapolis, MN: National Computer Systems, Inc.; 1993.

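### Aim 1 covariates are chosen by chance baseline imbalance instead of by relation to the outcome; a fixed, baseline-adjusted model would be a cheap improvement

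*Combined protocol and SAP*

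**What the plan says.** The opening paragraph of Statistical analyses states: "Preliminary analyses will compare study groups on demographic and other characteristics obtained in the screening and baseline assessments". The stated purpose is "to identify possible failures in random assignment, which would be statistically controlled for in subsequent analyses".

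The Aim 1 analysis is described as "performing a 2 (Condition) by 2 (Time) general linear model (GLM) analysis on the main outcome measures of working memory" and on delay discounting, with baseline and post-training as the two levels of Time and the Condition by Time interaction as the predicted effect. It is then repeated with the 1-month visit as a third level. No covariate is listed for either model.

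The only covariate named in advance belongs to a repeat: "All analyses will be repeated with other substance use added as a covariate". Its measure is not defined.

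The models are reused. For specificity, "we will use the same models to test for group differences on performance in other cognitive domains"; for Aim 3, "we will use the same GLM models described above to test for differences by condition on cocaine use".

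On allocation, Cognitive Training Sessions says "enrolled participants will be randomly assigned to either the experimental (Active Cognitive Training, or ACT) or control (or CON) conditions using simple random assignment". There are no stratification factors that could supply a covariate set.

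**The concern.** Adjusting for a covariate helps a randomised comparison when the covariate predicts the outcome. Whether the arms happen to differ on it is a separate matter. Under properly conducted simple randomisation every baseline difference is chance, so a rule triggered by imbalance will usually leave out a strong predictor that is balanced and may bring in a useless variable that is not.

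The plan also does not say what difference counts. Two analysts applying different cut-offs could fit different covariates to the primary comparison and occasionally reach different conclusions. Because the Aim 1 models are reused, the same rule reaches the 1-month, specificity and Aim 3 analyses.

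Meanwhile, the covariate most likely to be prognostic, the baseline score on the same outcome, is already collected but enters only as a level of Time. The two-by-two interaction test is then a test of change from baseline, which is less efficient than adjusting for baseline.

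**Working it through.** The plan states no sample size, power, alpha or imbalance threshold, so there is no figure to reproduce. Everything below other than the count in step 1 is illustrative.

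**1. Size of the pool.** Table 1 has 13 listings and Table 2 has 29, giving 42. Stimulant craving appears in both, leaving 41 distinct listings. These are not 41 instruments. Merging the two HVLT-R, two BVMT-R, two Trail Making and two SCID-5 listings and the three WAIS-IV subtests removes 1+1+1+1+2 = 6, leaving about 35. An analyst might compare far fewer, so a pool of 10 is shown alongside.

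**2. Chance of at least one flag under correct randomisation.** With k independent variables tested at an assumed 0.05, the chance is 1 − 0.95^k:
- k = 10: 0.40
- k = 35: 0.83
- k = 41: 0.88

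With an assumed mutual correlation of 0.3, simulation gives about 0.35 (k = 10) and 0.75 (k = 41).

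**3. Effect on the comparison.** Simulation assumptions: 60 participants, simple randomisation, baseline-to-post correlation 0.7, mutual correlation 0.3, 0.05 screen, true effect 0.5 SD. Flagged variables are added to the regression of change on condition. Prognostic means that several pool variables together explain part of the variance of change (14% or 29% was assumed).

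| Pool | Power, no adjustment | Power, imbalance rule | Verdicts differ |
|---|---|---|---|
| 10, not prognostic | about 0.68 | about 0.67 | about 4% |
| 41, not prognostic | about 0.67 | 0.61–0.63 | about 10% |
| 10, prognostic | 0.685 | 0.684 | 7–10% |
| 41, prognostic | 0.678 | 0.677 | up to about 27% |

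With the non-prognostic pools, the variance of the effect estimate rises by about 4% (pool of 10) and 13% (pool of 41). Type I error is about 0.05 with non-prognostic pools and 0.03 to 0.07 in the prognostic cells.

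**4. What the rule forgoes.** Take one covariate correlated 0.5 with change, 30 per arm, and an effect giving about 80% power unadjusted. The imbalance rule adjusts for it in about 5% of trials, and power stays at about 80%. Always adjusting gives 89%.

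**5. What baseline adjustment gains.** Let the outcome have variance s² at each visit and baseline-to-post correlation rho.
- Change: variance 2s²(1 − rho).
- Post-training value adjusted for baseline: variance s²(1 − rho²).
- Ratio: (1 − rho²) / [2(1 − rho)] = (1 + rho)/2.

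This is 0.75, 0.85 and 0.925 at assumed rho of 0.5, 0.7 and 0.85. At rho = 0.7 with 60 participants in equal arms and a 0.5 SD effect:
- Change: standard error √0.6 × √(4/60) = 0.200, so effect/SE = 2.50.
- Baseline-adjusted: standard error √0.51 × √(4/60) = 0.184, so effect/SE = 2.71.

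In simulation the variance ratio was 0.86 to 0.93, and power rose from 0.67–0.69 to 0.72–0.75. This gain is separate from the harm of the imbalance rule and does not measure it.

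**The case against.** The strongest case against runs as follows. Selection uses baseline data only, before any post-training outcome. The study calls itself a test of feasibility and preliminary efficacy. Every cost figure rests on an assumed sample size, cut-off and correlation structure. With a small pool the loss is trivial, and with prognostic candidates power does not fall. All of this stands, and it limits the weight of the point. It does not supply a reason to choose covariates by imbalance.

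Four stronger readings are tempting, and the documents do not support them.

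- **The rule inflates type I error.** A fixed rule of this kind stays near 0.05 in most settings. Error rises if someone tries several rules and keeps the most favourable: 0.07 to 0.10 with four rules, 36 independent candidates and 15 to 50 per arm. Nothing in the plan says that would be done.
- **Covariates are the only open part of the analysis.** They are not. Transformations also depend on the data, intent-to-treat is named without a rule for missing data, and no alpha is stated.
- **The unstated form of entry decides the result.** With complete data, a covariate entered only as a main effect leaves the Condition by Time test unchanged. However, a repeated-measures general linear model ordinarily gives a covariate its own coefficient at each time. The form is therefore less open than it looks, and the point does not rest on it.
- **Baseline is ignored.** It is used, but as a level of Time and not as a covariate.

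It can also be said that changing the primary model is a preference and that stating a criterion would be enough. A stated criterion would make the analysis reproducible, but covariates would still be selected by chance imbalance.

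**Conclusion.** The point holds as a cheap improvement. The plan contains an affirmative rule that selects covariates by observed imbalance under simple randomisation, without a criterion, and applies it to the primary comparison and to every analysis that reuses its models. A better method is available from data already collected.

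Under the stated assumptions the rule never helps much. Power is about unchanged at best and about 0.04 to 0.06 lower at worst (0.67 to 0.61–0.63, with a large non-prognostic pool). The larger practical effect is on reproducibility: whether adjustment is triggered changes the significance verdict in about 4% to 27% of trials at a 0.5 SD effect. The upper end needs a pool near 41 with prognostic content.

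These figures would move with the actual sample size, cut-off, pool and correlations, none of which the documents give. The logical point, that chance imbalance is not evidence of prognostic value, does not depend on them.

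**What to change.** In the opening paragraph of Statistical analyses, delete the provision that baseline comparisons trigger adjustment, and report baseline characteristics descriptively by arm.

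Under Aim 1, make the primary test the post-training outcome on condition, adjusted for the baseline value of the same outcome. Name any further covariates, chosen for their expected relation to that outcome, before data by arm are seen.

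Carry the same adjustment into the other models: for the 1-month analysis, for example, treat the post-training and 1-month values as repeated outcomes with baseline as covariate, and do likewise for the specificity and Aim 3 analyses.

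Keep the two-by-two Condition by Time model, imbalance-driven adjustment and the repeat with other substance use as labelled sensitivity analyses.

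The cost is analysis-plan wording across these models; no new data are needed. There are two downsides. A striking imbalance on an unlisted variable is adjusted for only in a sensitivity analysis. The hypothesis must also be restated as a baseline-adjusted comparison between arms instead of an interaction with Time.
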